### 3.6 Data Monitoring Committee (DMC)

No independent Data Monitoring Committee (DMC) is planned. Participant safety data will be continuously monitored by the Sponsor's internal safety management team (SMT), led by the Global Safety Officer, to detect any safety signals during the study period.

A separate SAP will be dedicated to SMT summaries and analysis.

## 4 Complementary Information on Assessment Methods

Study assessments and procedures are detailed in Section 8 of the protocol. This section focusses on complementary/additional information not detailed in the protocol.

### 4.1 Complementary Information for Endpoints Assessment Methods

Not applicable.

### 4.2 Complementary Information on Derived Endpoints: Calculation Methods

#### 4.2.1 Immunogenicity

##### 4.2.1.1 Computed Values for Statistical Analysis

For the derivation of immunogenicity endpoints, all values strictly under the lower limit of quantification (LLOQ) will be treated as LLOQ/2, and all values above or equal to the upper limit of quantification (ULOQ) will be treated as ULOQ.

For the analysis of the results of HIH assay, which is performed in duplicate, the individual geometric mean (GM) of both values will be computed for each blood sample and each strain, after managing extreme values as described above. The computed value is then considered the titer for that blood sample.

Only 1 titer value will be recorded for SN assay.

To appropriately manage extreme values (LLOQ and ULOQ) for analysis purposes, the following computational rule is applied to the values provided in the clinical database for each blood sample (BL) drawn:

For HAI

- If a value is  $<$  LLOQ, then use the computed value LLOQ/2
- If a value is between  $\geq$  LLOQ and  $<$  ULOQ, then use the value
- If a value is  $\geq$  ULOQ, then use the value ULOQ

For SN:

- If a value is  $<$  LLOQ, then use the computed value LLOQ/2
- If a value is between  $\geq$  LLOQ and  $<$  ULOQ, then use the value
- If a value is  $\geq$  ULOQ, then use the value ULOQ

#### 4.2.1.2 Fold-rise

For both the HAI and SN immune response, the derived endpoint fold-rise is driven by both baseline (D01) and post-baseline (D22 or D43) computed values as described in [Section 4.2.1.1](#) and is computed as individual ratio:

- 22 days after the last vaccination divided by D01.

Note: if pre-vaccination (D01) or post-vaccination (D22 or D43) values is missing, the fold-rise will be missing.

#### 4.2.1.3 Seroconversion

For HAI assay, seroconversion is defined as a binary indicator. If a pre-vaccination (D01) titer < 10 (1/dil): post-vaccination titer  $\geq$  40 (1/dil) on D43, or  $\geq$  4-fold-rise for participants with a pre-vaccination titer  $\geq$  10 (1/dil), the derived seroconversion indicator will be “Yes”, otherwise will be “No”.

For HAI assay, seroconversion is defined as a binary indicator. If a pre-vaccination (D01) titer < 10 (1/dil): post-vaccination titer  $\geq$  40 (1/dil) on D22, or  $\geq$  4-fold-rise for participants with a pre-vaccination titer  $\geq$  10 (1/dil), the derived seroconversion indicator will be “Yes”, otherwise will be “No”.

Note: if pre-vaccination (D01) or post-vaccination (D22 or D43) value is missing, the seroconversion is missing.

### 4.2.2 Safety

#### 4.2.2.1 Solicited Reactions

##### 4.2.2.1.1 Daily Intensity

All daily records for solicited reactions will be derived into daily intensity according to the following classification: None, Grade 1, Grade 2, Grade 3, or Missing (Unknown).

For the derivation of daily intensities, the following sequential steps will be applied:

- 1) For solicited reactions (except fever/pyrexia) with eCRF presence recorded as “No” and with all daily records missing (Unknown), all daily intensities will be derived as None.
- 2) For non-measurable solicited reactions, daily intensities will correspond to daily records reported in the clinical database. For measurable solicited reactions, the daily measurements reported in the clinical database will be converted based upon the intensity scales defined in the protocol; this assumes a reaction that is too large to measure (non-measurable, “NM”) is Grade 3.

The intensity could be considered “None” (not a reaction) in the analysis despite being considered a reaction by the investigator (e.g., swelling measurement  $>0$  mm but  $<25$  mm in adults).

Note: The maximum intensity of the ongoing period is derived from the record of the maximum intensity/measurement after the end of the solicited period following the rule described above.

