#### **8.3.2 Method of Detecting AEs and SAEs**

Individual eDiary, specifically designed for this study by the Sponsor and provided to the study sites, will be available to study participants for the recording of daily safety information. The eDiary is the primary method for safety data collection. However, paper diary cards will also be available for use as a back-up solution in case of major breakdown of the app or as determined by the Sponsor's study clinical team. The eDiary will include pre-listed terms and intensity scales as well as areas for free text to capture additional safety information or other relevant details.

Participants will also be provided with rulers for measuring the size of injection site reactions, and with standard digital thermometers for measuring daily temperatures. To ensure consistency of reporting, the study sites will instruct participants on how to correctly use these tools.

At specified intervals, the investigator or a designee will interview the participants to confirm the information recorded in the eDiary, and will attempt to clarify anything that is incomplete or unclear. All clinical study information gathered by the study site will be reported electronically using a web-based CRF. Any information that was not documented in the eDiary will first be captured in the source document and then reported electronically.

The 12-month follow-up should be done at least 365 days after the last vaccination for all participants having received at least one dose of the study intervention, by interviewing participants during Visit 5 (or over the telephone if the visit cannot be performed in-person) using a questionnaire to capture MAAEs, SAEs, and AESIs, if applicable.

Care will be taken not to introduce bias when detecting AEs and/or SAEs. Open-ended and non-leading verbal questioning of the participant is the preferred method to inquire about AE occurrences.

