##### **3.4.4.2.3 Intensity**

For solicited reactions, missing intensities will be handled as described in [Section 4.2.2.1.2](#). For unsolicited AEs, missing intensities will remain missing and will not be imputed.

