#### **4.2.2.1.2 Maximum Intensity**

Maximum overall intensity is derived from the daily intensities computed as described in [Section 4.2.2.1.1](#) and is calculated as the maximum of the daily intensities over the period considered.

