#### **4.2.2.1.3 Presence**

Presence is derived from the maximum overall intensity over the time-period considered:

- None: No presence
- Grade 1, Grade 2, or Grade 3: Presence
- Missing or Unknown: Missing presence

Participants with at least one non-missing presence for a specific endpoint will be included in the analysis. Conversely, those without a non-missing presence will not be included in the analysis of the endpoint.

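### SAP 4.2.2.1.1 keeps an eCRF 'No' without daily records as a non-reaction but lets an eCRF 'Yes' without daily records drop out, which lowers the rates of pain, headache, malaise and myalgia

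*SAP*

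**What the plan says.** SAP 4.2.2.1.1 derives daily intensities in sequential steps. Step 1 begins "For solicited reactions (except fever/pyrexia) with eCRF presence recorded as" 'No' and continues "and with all daily records missing (Unknown), all daily intensities will be derived as None". Step 2 covers everything else. For non-measurable reactions, "daily intensities will correspond to daily records reported in the clinical database". For measurable reactions, the recorded size is converted to a grade.

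The later sections carry the result forward:

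- SAP 4.2.2.1.2: the maximum intensity is "calculated as the maximum of the daily intensities over the period considered".
- SAP 4.2.2.1.3: presence follows from that maximum, with "Missing or Unknown: Missing presence". "Conversely, those without a non-missing presence will not be included in the analysis of the endpoint".
- SAP 3.4.3: the denominator for a solicited reaction is the participants with data for that endpoint.

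Two general provisions bear on the gap. SAP 3.4.4.2 says missing safety data are not replaced. SAP 3.4.4.2.3 says "For solicited reactions, missing intensities will be handled as described in" Section 4.2.2.1.2, but that section only takes a maximum and has no rule for missing values.

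**The concern.** Both answers are the same kind of evidence: a presence entry in the eCRF with no daily values behind it. The SAP accepts the entry when it is 'No' and gives it no effect when it is 'Yes'. Reported non-reactions stay in the denominator and reported reactions disappear.

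This also departs from how the SAP treats incomplete safety data elsewhere:

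- An unsolicited event counts if it has a verbatim term and is not Grade 0, so a missing grade does not remove it (4.2.2.2.1).
- An unsolicited event with missing onset stays in the 21-day tables (4.2.2.2.4).
- A missing causal relationship is counted as related (3.4.4.2.2).
- In the table of discontinuations by system organ class and preferred term, an unsolicited event may be Grade 1 or above or ungraded, whereas a solicited one must be at least Grade 1 (4.2.3.6).

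Solicited reactions are a listed secondary endpoint. SAP 3.5 says that safety is weighed with immunogenicity when the formulation is chosen after the Day 43 data. Reported reactogenicity that is too low would enter that choice.

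**Working it through.** The documents state no solicited-reaction rate and no missing-diary rate, so there is no planned figure to reproduce. The check traces each combination through the SAP and then sizes the effect under stated assumptions.

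**Trace (any solicited reaction except fever)**

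| eCRF presence | Daily records | Daily intensity | Presence | In the analysis? |
|---|---|---|---|---|
| No | all missing | None (step 1) | No | yes, as a non-reactor |
| Yes | all missing | Missing (step 2) | Missing | no |
| No or Yes | at least one | as recorded | from the maximum | yes |

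**Non-measurable reactions (pain, headache, malaise, myalgia)**

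Every grade in Protocol Tables 10.2 and 10.3 for these four is descriptive, and the lowest is Grade 1. A true 'Yes' is therefore a presence.

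Assumptions: p is the true rate; m is the share with an eCRF answer but no daily records; m is unrelated to reaction; eCRF answers are correct.

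- Reactors kept: p(1-m). Non-reactors kept: 1-p, because step 1 retains them all.
- Reported rate: R = p(1-m) / [p(1-m) + 1-p] = p(1-m)/(1-mp).
- Bias: R - p = -m·p(1-p)/(1-mp), which is never positive.

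| True p | m = 2% | m = 5% | m = 10% | m = 20% |
|---|---|---|---|---|
| 20% | 19.7% | 19.2% | 18.4% | 16.7% |
| 50% | 49.5% | 48.7% | 47.4% | 44.4% |
| 70% | 69.6% | 68.9% | 67.7% | 65.1% |

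The bias runs from -0.3 points (p = 20%, m = 2%) to -5.6 points (p = 50%, m = 20%).

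In counts, take 150 participants, the planned size of one age stratum in Group 1 or 2. Suppose 68 have daily records showing a reaction, 67 have records showing none, 7 have 'Yes' without records and 8 have 'No' without records. The SAP gives 68/(68+67+8) = 68/143 = 47.6%. Counting all answers gives (68+7)/150 = 50.0%.

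**Comparisons between groups**

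With the same m in both groups, a true difference of 70% against 40% is reported as 30.1, 30.2 and 30.3 points at m = 5%, 10% and 20%, so it barely moves. If m differs, a false difference appears: with p = 50% in both groups and m = 5% against 10%, it is 2.63 - 1.28 = 1.35 points.

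**Size-graded reactions (erythema, swelling, induration, ecchymosis)**

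Presence here needs at least 25 mm, and SAP 4.2.2.1.1 notes that a smaller reaction reported by the investigator is analysed as None. An unmeasured 'Yes' is thus not a known event. Let P and N be participants with records (present, none), Nm those with 'No' and no records, Ym those with 'Yes' and no records, and k the number of Ym that reached 25 mm.

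- Reported: P/(P+N+Nm).
- True graded rate: (P+k)/(P+N+Nm+Ym).
- The reported rate is too low only if k/Ym exceeds it.

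Example with P = 20, N = 110, Nm = 8, Ym = 12 (150 in all). Reported: 20/138 = 14.5%.

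| k | True graded rate | Reported minus true |
|---|---|---|
| 0 | 20/150 = 13.3% | +1.2 points |
| 1 | 21/150 = 14.0% | +0.5 |
| 2 | 22/150 = 14.7% | -0.2 |
| 12 | 32/150 = 21.3% | -6.8 |

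**The case against.** The strongest reply is that the problem case may be rare or may not exist. The trigger is missing daily records in the clinical database, not a missing eDiary. Protocol 8.3.2 provides paper cards as back-up and a site interview, and adds: "Any information that was not documented in the eDiary will first be captured in the source document and then reported electronically". That route could supply daily values, and a single day at Grade 1 or above is enough for presence. The documents do not say whether the eCRF accepts a 'Yes' with no daily value. This stands as a limit on the size. It does not close the gap, because step 1 itself presupposes presence answers without daily records, and exclusion of the matching 'Yes' follows from the text.

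A second reply is scale. The safety analyses are descriptive. At m = 5% the bias is at most 1.3 points, whereas the Clopper-Pearson interval for 90/150 runs from 51.7% to 67.9%. That is fair for small m. But the bias in the four non-measurable reactions has a known sign, the interval does not reflect it, and removing it costs little.

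A reader might also infer that every solicited rate except fever is biased downward and can move no other way. The documents do not support that. Four of the eight non-fever reactions are size-graded, and for these the bias can be upward. Participants with neither an eCRF answer nor daily records are also excluded, and they can shift any rate in either direction.

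**Conclusion.** The asymmetry is in the SAP as written, and no other section repairs it. For pain, headache, malaise and myalgia the rule can only lower the reported rate, as long as eCRF answers are correct. The loss is about 1 point at m = 5% and up to 5.6 points at m = 20%. Those sizes rest wholly on assumed values of m and on missingness unrelated to reaction. For erythema, swelling, induration and ecchymosis the direction is not determined. Comparisons between groups are affected mainly if m differs between them, and nothing in the documents shows that it will. The point is worth correcting before the Day 43 unblinding. If the eCRF cannot hold a 'Yes' without daily records, a sentence saying so would settle the effect on the rates.

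**What to change.** In SAP 4.2.2.1.1 and 4.2.2.1.3, add the mirror of step 1: an eCRF 'Yes' with all daily records missing gives presence = Yes with grade missing. Then:

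- For pain, headache, malaise and myalgia, count these participants in the numerator and denominator of the 'any' row, with a separate 'grade missing' row.
- For erythema, swelling, induration and ecchymosis, show the rate with and without them.
- Report the number of 'Yes' answers without daily records by group and age stratum.
- Reconcile step 1 with the no-replacement statement in 3.4.4.2, and point 3.4.4.2.3 to the section that holds the rule.

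Removing step 1 would also treat the two answers alike, but it is not a safe substitute. The eCRF is not shown, and a 'No' may normally leave the daily entries blank. If half of true non-reactors had such records (an assumption), a true 30% would be reported as 0.30/(0.30 + 0.35) = 0.30/0.65 = 46%.

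The cost is a few sentences in the SAP and one derivation line. The downside is an extra 'grade missing' row and slightly higher reported rates.

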#### **4.2.2.1.2 Maximum Intensity**

Maximum overall intensity is derived from the daily intensities computed as described in [Section 4.2.2.1.1](#) and is calculated as the maximum of the daily intensities over the period considered.

#### **4.2.2.1.3 Presence**

Presence is derived from the maximum overall intensity over the time-period considered:

- None: No presence
- Grade 1, Grade 2, or Grade 3: Presence
- Missing or Unknown: Missing presence

Participants with at least one non-missing presence for a specific endpoint will be included in the analysis. Conversely, those without a non-missing presence will not be included in the analysis of the endpoint.

#### **4.2.2.1.4 Time of Onset**

Time of onset is derived from the daily intensities computed as described in [Section 4.2.2.1.1](#). It corresponds to the first day with intensity of Grade 1, Grade 2, or Grade 3.

Note: If a reaction is not continuous (i.e., reaction occurs over two separate periods of time intervened by at least one daily intensity Missing or None), then the time of onset is the first day of the first occurrence.

Time of onset period is displayed as D01-D04 and D05-D08 after vaccination.

#### **4.2.2.1.5 Number of Days of Occurrence During the Solicited Period**

Number of days of presence over the period considered is derived from the daily intensities computed as described in [Section 4.2.2.1.1](#). It corresponds to the number of days with daily intensities of Grade 1, Grade 2, or Grade 3. Number of days of presence over the solicited period with a specified intensity may also be derived.

#### **4.2.2.1.6 Overall Number of Days of Occurrence**

If a reaction is ongoing at the end of the solicited period, then the overall number of days of presence is derived from the daily intensities and the end date of the reaction after the end of the solicited period. The overall number of days of presence is:

- $(\text{End date} - \text{last vaccination date}) + (\text{number of days of presence within the solicited period}) - \text{length of the solicited period} + 1$

If the end date is missing or incomplete (contains missing data), the overall number of days of presence will be considered as Missing.

#### 4.2.2.1.7 Ongoing

Ongoing is derived from the last daily intensity of the solicited period computed as described in [Section 4.2.2.1.1](#), and the maximum intensity on the ongoing period. The investigator's ongoing flag is not used because the measurement will determine the ongoing status of the reaction.

- Ongoing: if the last daily intensity of the solicited period is at least Grade 1 and the maximum intensity on the ongoing period is at least Grade 1.
- Not ongoing: if the last daily intensity of the solicited period is None or the maximum intensity on the ongoing period is None.
- Missing: all other conditions (in this case, it is not included in the denominator of the ongoing analysis in the safety tables).

#### 4.2.2.2 Unsolicited AEs

##### 4.2.2.2.1 Presence

An observation will be considered an event if it has at least a verbatim term and is not a Grade 0 intensity event.

Grade 0 events are not included in safety analysis but are included in separate listings.

##### 4.2.2.2.2 Intensity

Intensity will be derived according to the following classification: None, Grade 1, Grade 2, Grade 3, or missing.

If the unsolicited AE is measurable and its preferred term is part of the list of solicited reactions, then the measurement is derived based upon and following the same rule of the intensity scales defined in the protocol for that measurable injection site or systemic reaction. Note the intensity could be considered as "None" (not a reaction) in the analysis despite being considered a reaction by the investigator (e.g., swelling measurement  $> 0$  mm but  $< 25$  mm).

Intensity for the other unsolicited AEs will correspond to the value reported in the eCRF.

The maximum intensity corresponds to the highest intensity for a unique term.

##### 4.2.2.2.3 Last Vaccination

Last vaccination before an unsolicited AE will be derived from the pre-visit numbers provided in the clinical database and will be calculated as follows:

- If an unsolicited AE has a non-missing pre-visit number, the pre-visit number will be used to determine the last vaccination before the unsolicited AE.

- If the pre-visit number is missing and the start date is complete (i.e., including the day), then the start date will be used to determine the last vaccination before the unsolicited AE.
- If an unsolicited AE has a missing pre-visit number and a partial start date (at least the day missing), the unsolicited AE will be considered as post injection 1.

#### 4.2.2.2.4 Time of Onset

Time of onset is derived from the start date of the unsolicited AE and the date of vaccination:

Time of Onset = start date of the unsolicited AE - date of vaccination + 1 (if D01 is the first vaccination day).

The time of onset is considered as missing only if one or both dates are missing or partially missing.

The unsolicited AEs will be analyzed “Within 21 days” after each vaccination, which corresponds to AEs with a time of onset between D01 and D22 or missing. An AE with missing time of onset will be considered to have occurred just after the vaccination, so will be included in these tables.

Time of onset period is displayed as D01-D04, D05-D08, D09-D15, D16 or later, and missing.

**Note:** Unsolicited AE that occurred before vaccination (negative time of onset) or with a time of onset higher than defined above will not be included in analysis but will be listed separately.

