##### **3.4.4.2.4 Start Date and End Date**

Missing or partially missing start dates or end dates for unsolicited AEs (including SAEs) will remain missing and not be imputed. If the start date is missing or partially missing, the time of onset will be set to missing. If either the start date or end date is missing or partially missing, the duration will be considered missing.

Missing or partially missing end dates for ongoing solicited AEs will remain missing and not be imputed.

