#### 4.2.2.2.6 Serious Adverse Events

An event will be considered as a serious event if “Yes” is checked for “Serious?” in the eCRF. SAEs will be analyzed within 21 days after each vaccination, from D22 to 387 days after each vaccination, and within 387 days after each vaccination.

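### The SAP counts unsolicited AEs with a partial start date as early onset, and some as post injection 1, without checking the known month

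*SAP*

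**What the plan says.** Four SAP rules act together.

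- **SAP 3.4.4.2.4 (Start Date and End Date):** the rule for incomplete dates is "Missing or partially missing start dates or end dates for unsolicited AEs (including SAEs) will remain missing and not be imputed". It continues: "If the start date is missing or partially missing, the time of onset will be set to missing".
- **SAP 4.2.2.2.4 (Time of Onset):** the 21-day analysis is defined by the phrase "which corresponds to AEs with a time of onset between D01 and D22 or missing". The reason given is that "An AE with missing time of onset will be considered to have occurred just after the vaccination".
- **SAP 4.2.2.2.3 (Last Vaccination):** where a pre-visit number exists, "the pre-visit number will be used to determine the last vaccination before the unsolicited AE". Failing that, a complete start date is used. The last case is an event with a "missing pre-visit number and a partial start date (at least the day missing), the unsolicited AE will be considered as post injection 1".
- **SAP 4.2.2.2.6 (Serious Adverse Events):** "SAEs will be analyzed within 21 days after each vaccination", then from D22 to 387 days, and within 387 days. SAP 4.2.2.2.7 gives AESIs the same three windows. Neither section says what to do when onset is missing.

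Protocol 10.3.1 counts SAEs among the unsolicited AEs. Protocol 8.3.1 collects SAEs until 12 months after the last vaccination, but non-serious unsolicited AEs only to 21 days after each dose.

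**The concern.** A start date with only the day missing still carries information, often enough to settle the window and the dose. The SAP discards it. An SAE recorded as starting in a month far beyond the second dose is treated like one with no date at all and enters the 21-day table. If its pre-visit number is missing, it is also attributed to injection 1.

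That entry would contradict the trial's own data. It would overstate early SAEs or AESIs and understate the D22-387 window, because a missing onset is assigned only to the early one. It could also move an event from the second dose to the first.

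The SAP's wording also pulls two ways. Section 3.4.4.2.4 says dates are not imputed, yet section 4.2.2.2.4 in effect assigns an onset right after vaccination.

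**Working it through.** The plan gives no figure to reproduce. The check is a trace of the rules, followed by simple date arithmetic.

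**1. Trace with assumed dates.** Dose 1 on 1 September 2022, dose 2 on 22 September 2022, SAE start recorded only as March 2023. By the SAP 4.2.2.2.4 formula, onset = start date − vaccination date + 1:

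| | Earliest (1 March) | Latest (31 March) |
|---|---|---|
| After dose 1 | D182 | D212 |
| After dose 2 | D161 | D191 |

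Every possible day lies outside D01-D22 for either dose and after dose 2. Under the SAP:

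- Onset is missing (3.4.4.2.4).
- Applying 4.2.2.2.4, the event enters the 21-day table.
- With a pre-visit number, it enters that table for the dose so identified. Without one, it enters as post injection 1 (4.2.2.2.3).
- The Note in 4.2.2.2.4 that removes events outside the window needs a computed onset, so it cannot catch this event.

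**2. Share of follow-up outside both 21-day windows.** On schedule, dose 2 is on D22 and the two windows together cover D01-D43. The rest is 387 − 43 = 344 days, and 344/387 = 88.9%.

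**3. Share that a month check could identify.** Assume SAE onsets spread evenly over D01-D387, first doses spread evenly over a calendar year, dose 2 exactly 21 days later, and only the day of onset unknown. The month excludes a window only if its first day falls after the window ends. This loses, on average, the number of days already elapsed in the month:

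- Mean of (day of month − 1) = [7 × (31 × 30/2) + 4 × (30 × 29/2) + 28 × 27/2] / 365 = (3,255 + 1,740 + 378)/365 = 14.72.
- Month excludes both 21-day windows: (344 − 14.72)/387 = 85.1%.
- Month begins after dose 2 (after D22), so injection 1 cannot be the last dose: (365 − 14.72)/387 = 90.5%.

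Direct enumeration over all start dates and onset days gives the same 85.1% and 90.5%.

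**4. Effect of one event.** On planned stratum sizes, one misplaced SAE moves a rate by 1/150 = 0.67 percentage points in Group 1 or 2, and by 1/50 = 2 points in Group 3.

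**5. Non-serious unsolicited AEs.** These are collected only to 21 days after each dose, so the shares in steps 2 and 3 do not apply to them. The 21-day default matches their collection period. What can go wrong is the dose, when the pre-visit number is missing and the known month falls after dose 2.

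**The case against.** **Does the placement rule reach SAEs at all?** A reader might infer that the SAP expressly puts partially dated SAEs in the 21-day window. It does not. Section 3.4.4.2.4 names SAEs only for leaving dates unimputed and setting onset to missing. Section 4.2.2.2.4 speaks of unsolicited AEs, and its Note removes events with a later onset from analysis. That cannot hold literally for SAEs, which 4.2.2.2.6 analyses to 387 days. So applying the default to SAEs and AESIs is an inference. It is a well-supported one: the protocol defines SAEs as unsolicited AEs, both sections sit under the SAP's Unsolicited AEs heading, and neither has a rule of its own. On the alternative reading, a partially dated SAE has no defined place in any window, which also needs repair.

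**Few events, and visible ones.** SAEs are reported within 24 hours (Protocol 8.3.1), the investigator reviews the records (Protocol 10.3.3) and data are cleaned before the main lock (SAP 3.5). Partial dates may be rare. The onset display keeps a missing category, and the event still counts within 387 days. All of this stands and limits the consequence.

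**A cautious default.** Missing causality is taken as related (SAP 3.4.4.2.2), so counting uncertain events as early fits the SAP's general approach. That is sound for a wholly missing date. It does not justify an early entry when the recorded month excludes it, and it is not cautious for the late window.

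**Conclusion.** The point holds, within limits. The SAP has no check against the known month and year. Following it can give a 21-day entry, and with a missing pre-visit number an injection 1 attribution, that the recorded date contradicts. The effect falls mainly on SAEs and AESIs.

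The 85% and 91% are conditional on a partial date and rest on the even-spread assumptions above. The absolute number is unknown, because the documents give no expected count of partial dates.

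Three stronger conclusions are not supported:

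- **That about 89% of all partially dated AEs go to the wrong window.** The collection period rules this out for non-serious events.
- **That partially dated events go to injection 1 as a matter of course.** The pre-visit number takes priority, and the default needs both gaps.
- **That dose selection is at risk.** The analysis for that purpose uses data up to 21 days after the last vaccination (SAP 3.5), so late events bear on the final report only.

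This is a flaw in a derivation rule for descriptive safety tables. It is worth correcting because it is cheap to do so.

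**What to change.** Amend SAP 3.4.4.2.4, 4.2.2.2.3 and 4.2.2.2.4. Keep dates unimputed, keep the pre-visit number as the first source for the dose, and keep the current rule for wholly missing dates. When the start date is partial, compare the known month and year with the vaccination dates:

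- **(a)** If compatible with the 21-day window of the assigned dose, keep the current default.
- **(b)** If wholly after that window, place SAEs and AESIs in the D22-387 window. List other unsolicited AEs separately, as the Note in 4.2.2.2.4 already does for late onsets.
- **(c)** If wholly before dose 1, list separately as pre-vaccination.
- **(d)** If the pre-visit number is missing, assign injection 1 only when the partial date allows onset before dose 2. Otherwise assign injection 2, where it was given.

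State that this governs the windows in 4.2.2.2.6 and 4.2.2.2.7, and describe the remaining 21-day default as a window-assignment convention so that it no longer conflicts with the no-imputation statement.

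The cost is a short SAP edit and a minor change to the derivation program. No new data are needed.
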